2.1. Study Design

This will be a randomized, double-blind, placebo-controlled, multicenter study to compare two doses of varenicline 1 mg BID and 0.5 mg BID with placebo for smoking cessation in adolescent smokers aged 12-19 years who are motivated to quit. Since varenicline exposure is related to body weight, subjects with a body weight ≤ 55 kg will have their varenicline dose reduced by half (those randomized to 1 mg BID will receive 0.5 mg BID and those randomized to 0.5 mg BID will receive 0.5 mg QD).

[figure not shown]
Randomization will be stratified by age group (12-16 vs 17-19) and body weight. In order to ensure a sufficient number of subjects in the 12-16 year old stratum, the 17-19 year old stratum will be capped at a maximum of 90 subjects.

Those subjects deemed eligible will be randomized and enter the 12-week placebo-controlled treatment period with weekly clinic visits for efficacy and safety assessments and smoking cessation counseling. Varenicline or placebo dosing will begin with two weeks of titration. (Figure 1). All subjects will set a target quit date (TQD) to coincide with the Week 1 visit. The Week 1 visit occurs at the end of the first week of the treatment phase. The primary efficacy endpoint will be complete abstinence from smoking, biochemically verified, during the last 4 weeks of the 12 week dosing period.

Follow-up period: Subjects will be followed to obtain smoking status for 9 months after the end of the 12-week treatment period. Clinic visits will occur at Weeks 13-16 (inclusive), 20, 28, 36, 44, and 52. Telephone visits are planned for Weeks 24, 32, 40, and 48.

The clinical trial is illustrated in [Figure 1](#).

Figure 1. Study A3051073 Trial Diagram

2.2. Study Objective

To evaluate the efficacy, safety, and tolerability of varenicline compared with placebo in adolescent smokers aged 12-19 years.

3. INTERIM ANALYSES, FINAL ANALYSES AND UNBLINDING

No interim analyses are planned for this study. The final analysis will be first performed at database release.

A Data Monitoring Committee will be used to monitor unblinded safety data in an ongoing manner.

4. HYPOTHESES AND DECISION RULES

4.1. Statistical Hypotheses

The primary hypotheses of interest are designed to assess the efficacy objective of this study, and are as follows;

1 mg BID group vs. placebo

$$H_0 : OR = 1$$

$$H_1 : OR \neq 1$$

0.5 mg BID group vs. placebo

$$H_0 : OR = 1$$

$$H_1 : OR \neq 1$$

where OR is the odds ratio (relative to placebo) of continuous abstinence from Week 9 to Week 12 (the last 4 weeks of treatment). The OR will be evaluated using a logistic regression model based on the predicted Week 9-12 continuous abstinence rate (CAR).

4.2. Statistical Decision Rules

Statistical hypotheses for the primary endpoint will be tested in an ordered fashion to preserve overall Type I Error. The 1 mg BID group will be tested against placebo, and if a statistically significant difference is observed, the 0.5 mg BID group will be tested against placebo. A p-value of 0.05 or smaller will be considered statistically significant in both tests. Both tests will be presented regardless of the p-value obtained.

P-values will be reported with no adjustments for the analysis of multiple secondary endpoints or analyses by strata.

5. ANALYSIS SETS

In each of the following efficacy populations, subjects who discontinue the study are assumed to be smokers from the time point of discontinuation through the end of the study.

In computing responder rates, subjects who discontinue the study will be included in the denominator but not in the numerator, regardless of their last smoking status evaluation.

5.1. Full Analysis Set

The primary efficacy analysis population will be the Full Analysis Set, defined as all subjects who were randomized.

5.2. Completer Subjects Analysis Set

The Completer Subjects population is defined as the subset of the Full Analysis Set who have at least 80% treatment compliance, as measured by having any dose of study medication for 80% of the planned number of days in the trial treatment period.

5.3. Safety Analysis Set

The Safety Analysis population will be all subjects who took at least 1 dose of randomized study medication, including partial doses.

5.4. Treatment Misallocations

Errors in treatment allocation will be handled in the following way:

If a subject was:

- Randomized but not treated, are excluded from all safety analyses as actual treatment is missing but will be included in the Full Analysis Set for the primary efficacy analysis.
- Treated but not randomized, will be excluded from the efficacy analyses since randomized treatment is missing, but will be reported under the treatment they actually received for all safety analyses.
- Randomized but took incorrect treatment, will be reported under their randomized treatment group for all efficacy analyses, but will be reported under the treatment they actually received for all safety analyses.

5.5. Protocol Deviations

The definitions of the Full Analysis Set and Completer populations are based only on patient treatment compliance as described in Sections 5.1 through 5.2. Violations of the protocol inclusion or exclusion criteria or other protocol violations or deviations will not exclude subjects from the defined analysis populations.

A summary by treatment group as well as a list of all clinically important protocol deviations will be included in the study report.

5.6. Compliance

The definition of compliance for the purpose of assessing the extent to which patients are complying with the prescribed dosing for the entire trial treatment period is as follows:

$$\text{Compliance} = \frac{\text{Actual number of tablets taken}}{\text{Expected number of tablets to be taken}}, \text{ where}$$

Actual number of tablets taken is as per the dosing log in the CRF and expected number of tablets taken is the number of tablets prescribed.

Note that this is not the definition of compliance as used for the Completers Population, which requires only that patients take any amount of study drug for 80% of the planned number of days in the trial treatment period.

6. ENDPOINTS AND COVARIATES

6.1. Efficacy Endpoint(s)

Efficacy assessments will include measurement of smoking cessation and reduction obtained from the Nicotine Use Inventory (NUI) and urine cotinine measurements. The Week 24, 32, 40, and 48 visits are telephone visits, and therefore do not include collection of urine cotinine. Abstinence rates based on or including these visits do not require chemical confirmation. Urine cotinine is collected at all in-person clinic visits, and all abstinence rates based on in-clinic visits utilize urine cotinine to confirm abstinence. The reduction in the number of cigarettes smoked is based solely on the reported number of cigarettes on the NUI at baseline and the post-baseline visit of interest. The endpoints derived from these include:

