7. ASSESSMENTS

7.1. Efficacy

7.1.1. Smoking Status

Smoking status will be assessed using a standard series of questions referred to as the Nicotine Use Inventory (NUI) ([Appendix 1](#)). The subject responds Yes or No to questions about cigarette or other nicotine/tobacco use since the last visit or during the past 7 days. The NUI is completed at each clinic visit and/or phone contact during the treatment period and the follow-up period by research staff based on subjects' responses.

All subjects will be provided with Smoking Diary Worksheets to use as a tool to record how many cigarettes they have smoked each day. The Smoking Diary itself will not be data-based.

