7.3.2. Shipment of PK Samples

The shipment address and contact information will be provided to the investigator site prior to initiation of the trial.

Every effort should be made to ensure that the protocol required tests and procedures are completed as described. However, it is anticipated that from time to time there may be circumstances, outside the control of the investigator that may make it unfeasible to perform the test. In these cases the investigator will take all steps necessary to ensure the safety and well-being of the subject. When a protocol required test cannot be performed the investigator will document the reason for this and any corrective and preventative actions which he/she has taken to ensure that normal processes are adhered to as soon as possible. The study team will be informed of these incidents in a timely fashion.

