8.2. Statistical Analyses

All efficacy analyses will be based on the Full Analysis Set as described in [Section 5.1](#). Efficacy analyses will also be performed on the Completer Set as described in [Section 5.2](#). Missing values will be handled as explained in [Section 7](#).

All analyses will be performed overall as well as on the age stratum of patients who are 12-16 years of age (with corresponding removal of age strata terms from analysis models).

Subjects in this adolescent study will be considered smokers, regardless of the self reported smoking status, if the urine cotinine test is positive.

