As a sensitivity analysis of the primary endpoint, multiple imputation methods will be used to evaluate the impact of missing data. Subjects who discontinue the study due to insufficient clinical response, adverse event, or death will be imputed based upon the observed placebo distribution, regardless of randomized treatment assignment. Imputation will be based on age stratum, body weight stratum, pooled study center, and baseline number of cigarettes smoked. Subjects who discontinue the study for other reasons, or who complete the study but have a missing Week 9-12 CAR, will be imputed based on observed subjects in the same treatment group. Imputation will be based on treatment, age stratum, body weight stratum, pooled study center, and baseline number of cigarettes smoked.

A final sensitivity analysis will be performed based on discontinuation from treatment, regardless of study completion status.

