- 12-16 year old age stratum, ≤ 55 kg weight stratum (without age strata or body weight strata covariates).
- 12-16 year old age stratum, > 55 kg weight stratum (without age strata or body weight strata covariates).

8.2.4.3. The Continuous Abstinence Rate from Week 9 through Week 24 and Week 52

The continuous abstinence rate at a given time point will be defined as the proportion of subjects who remained abstinent from Week 9 through the time point being summarized.

The continuous abstinence rates from Week 9 through Week 24 and Week 9 through Week 52 will be summarized by treatment group using descriptive statistics and bar charts.

These will be summarized for the following groups:

- Overall study.
- 12-16 year old age stratum.
- 12-16 year old age stratum, ≤ 55 kg weight stratum.
- 12-16 year old age stratum, > 55 kg weight stratum.

- 17-19 year old age stratum.

The continuous abstinence from Week 9 through Week 24 and from Week 9 through Week 52 endpoints will be analyzed using separate logistic regression models as described in [Section 8.1.1.2](#). Odds ratios and 95% confidence intervals will be shown in plots.

These will be analysed for the following groups:

- Overall study.
- 12-16 year old age stratum (without age strata covariate).
- 12-16 year old age stratum, ≤ 55 kg weight stratum (without age strata or body weight strata covariates).
- 12-16 year old age stratum, > 55 kg weight stratum (without age strata or body weight strata covariates).

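### SAP 6.1 waives cotinine confirmation for any abstinence rate that includes a phone visit, which read literally exempts all of CAR 9-24 and CAR 9-52 and conflicts with SAP 8.2 and protocol 9.1

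*SAP*

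**What the plan says.** SAP 6.1 identifies Weeks 24, 32, 40 and 48 as telephone visits at which no urine is collected. It continues: "Abstinence rates based on or including these visits do not require chemical confirmation". The following sentence says that cotinine is collected at all in-person visits and that "all abstinence rates based on in-clinic visits utilize urine cotinine to confirm abstinence". Neither sentence says which one governs a rate built from both kinds of visit.

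SAP 8.2, which introduces all the analyses, sets a general rule: "Subjects in this adolescent study will be considered smokers, regardless of the self reported smoking status, if the urine cotinine test is positive". It makes no exception for any endpoint. SAP 8.2.4.3, which defines the two long-term rates, describes them only as "the proportion of subjects who remained abstinent from Week 9 through the time point being summarized" and does not mention cotinine.

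On the protocol side, section 7.1.2 schedules site cotinine tests at Weeks 9-12 and at every follow-up clinic visit, for the stated purpose of confirming self-report. The efficacy text in section 9.1, immediately after it refers to the secondary endpoints, says they rest on self-report with cotinine confirmation. It has no telephone exception.

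The primary endpoint is described separately in SAP 2.1: "The primary efficacy endpoint will be complete abstinence from smoking, biochemically verified, during the last 4 weeks of the 12 week dosing period".

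**The concern.** The reason for the waiver is practical: urine cannot be collected by phone. That reason justifies relying on self-report at the phone contacts. It does not justify dropping a confirmation that is scheduled and collected at the clinic visits in the same window. The sentence does not stop at rates based on phone visits; it extends to rates that merely include one, and that takes in CAR 9-24 and CAR 9-52 entirely.

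These are the trial's only long-term continuous-abstinence endpoints. If a programmer follows the waiver as worded, they become self-report endpoints. If another follows SAP 8.2 or protocol 9.1, they are cotinine-checked at every clinic visit. The documents support both derivations, so the responder counts could depend on who reads them.

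**Working it through.** The documents give no figure for the share of phone contacts, so there is nothing to reproduce. The check is a count from the visit schedule, followed by a comparison of the rules.

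**Inputs.**
- Clinic visits with scheduled cotinine during treatment: Weeks 9, 10, 11, 12 (protocol Table 1, 6.2.2, 7.1.2).
- Clinic visits with scheduled cotinine in follow-up: Weeks 13, 14, 15, 16, 20, 28, 36, 44, 52 (protocol 3, 6.3.1, 7.1.2).
- Telephone contacts without cotinine: Weeks 24, 32, 40, 48 (protocol 6.3.2, SAP 6.1).

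**Counts, both end weeks included.**
- CAR 9-12: 4 clinic + 0 phone = 4 contacts. The waiver does not reach it.
- CAR 9-24: clinic Weeks 9-16 (8 visits) and 20 (1) = 9; phone Week 24 = 1; total 10. Clinic share 9/10 = 90%, phone share 1/10 = 10%.
- CAR 9-52: the 9 clinic visits above plus Weeks 28, 36, 44, 52 = 13; phone = 4; total 17. Clinic share 13/17 = 76%, phone share 4/17 = 24%.

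Of the clinic tests, 4 are the Week 9-12 tests shared with the primary endpoint, leaving 9 - 4 = 5 and 13 - 4 = 9 after treatment. Leaving out the Week 9 visit would give phone shares of 1/9 and 4/16, but cotinine is scheduled at Week 9, so the inclusive count fits. The Week 22 entry in SAP 6.3 is a window for assigning early-termination visits, not a scheduled contact.

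**How each rule classifies a subject.** Take a retained subject who reports abstinence at every contact and has an unusual result at the Week 20 clinic visit, which lies in both windows.

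| Rule followed | Week 20 test positive | Week 20 test missing |
|---|---|---|
| SAP 6.1 waiver taken literally | responder | responder |
| SAP 6.1 waiver, with SAP 8.2 overriding | smoker | responder |
| Protocol 9.1, or the second sentence of SAP 6.1 | smoker | not settled: no missing-test rule |

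The rules disagree in the first column, and the second column has no stated answer under the third rule.

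**Reach beyond the two endpoints.** SAP 6.4 begins the pooling of small centers from a center-by-CAR 9-52 table in the completers and checks convergence on the CAR 9-52 model. The pooled centers are a covariate in the primary logistic model (SAP 8.1.1.2). A different derivation of CAR 9-52 could therefore change the pooling used in the primary analysis, even though no subject's Week 9-12 responder status changes.

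**The case against.** The best defense is that SAP 8.2 already settles the matter. It is the parent section of 8.2.4.3, it makes a positive cotinine test decisive whatever the subject reports, and it has no exception. A subsection need not repeat its parent's rule. The second sentence of SAP 6.1 and protocol 9.1 point the same way. The SAP's log entry for version 1.1 speaks only of rates based on the telephone data; it carries little weight, but it suggests that a narrow waiver was meant. The Statistical Rulebook named in protocol 9 is not among the documents and may hold the exact derivation. And for 7-day point prevalence at Week 24, which rests on a phone contact alone, a waiver is unavoidable.

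Much of this stands. SAP 8.2 probably prevents the worst case. It does not remove the conflict. SAP 6.1 is the more specific text on these rates and could be taken as the exception to a general rule. SAP 8.2 also acts only on a positive test; it does not require that a test exist.

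Three stronger readings are tempting, and the documents do not support them.
- *The long-term rates will be analyzed on self-report alone.* SAP 8.2 stands against this. It is a possible derivation, not an established one.
- *A subject can count for CAR 9-52 without counting for CAR 9-12.* Once SAP 8.2 is applied, this needs a rule that a missing Week 9-12 cotinine fails the primary endpoint, and no such rule is stated. SAP 7 covers only subjects who discontinue the study. The imputation text in SAP 8.2.3 mentions subjects "or who complete the study but have a missing Week 9-12 CAR", but does not say that a missing cotinine is the cause. The verification wording in SAP 2.1 sets no missing-test rule. Loss of nesting is possible, not shown.
- *Missing clinic tests are to be expected.* Protocol 7.3.2 closes with general text on circumstances "outside the control of the investigator that may make it unfeasible to perform the test", which applies to any protocol test. Protocol 7.1.1 says "The NUI is completed at each clinic visit and/or phone contact during the treatment period and the follow-up period", but that is generic wording, and no phone contacts are scheduled in Weeks 9-12. Neither indicates how often an on-site urine test would be missed.

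**Conclusion.** The waiver in SAP 6.1 is worded more broadly than its reason allows and contradicts other stated rules. Read literally, it removes confirmation from 9 of 10 contacts in CAR 9-24 and 13 of 17 in CAR 9-52 at which a cotinine test is scheduled. The resulting ambiguity affects who counts as a responder for both endpoints and, through SAP 6.4, the center pooling. The wording and the counts are certain.

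The consequence is less certain. The documents do not allow the size or direction of any effect on the odds ratios to be determined. The responder definition for the primary endpoint is unaffected. The conclusion assumes that no derivation outside these documents, such as the Statistical Rulebook, already resolves the conflict. Even if one does, the SAP sentence still says more than it should. The point merits correction because the change is small and restores a confirmation that the protocol already calls for.

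**What to change.** In SAP 6.1, replace the waiver with: *Telephone contacts contribute self-report only; urine cotinine applies at every clinic visit within the window.*

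In SAP 8.2.4.3, state that a CAR 9-24 or CAR 9-52 responder:
- must be a CAR 9-12 responder;
- must report no smoking since the last contact at the later contacts in the window;
- must have no positive cotinine at any clinic visit in the window.

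The second condition should follow the form of the follow-up Nicotine Use Inventory (protocol Appendix 1), which asks about the whole interval since the previous contact. A later answer can then cover a missed call, and one missed call need not disqualify a subject.

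Also state one explicit rule for a missing clinic cotinine and apply it alike to CAR 9-12, CAR 9-24 and CAR 9-52. The SAP has no such rule now, so a cross-reference to the primary endpoint would not be enough.

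The cost is a few sentences of SAP text and one derived flag, using data already scheduled for collection. The long-term rates may be slightly lower. A subject using nicotine replacement in follow-up, which protocol 4.4 restricts only during treatment, could test positive and count as a smoker; SAP 8.2 as written already has that effect.

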6.1.1. Primary Efficacy Endpoint

- *4-week continuous abstinence rate (CA) from Week 9 through Week 12 of treatment for varenicline compared with placebo.*

6.1.2. Secondary Efficacy Endpoints

- *7-day point-prevalence of smoking abstinence at Weeks 12, 24, and 52;*
- *Reduction in number of cigarettes smoked at Weeks 12, 24, and 52;*
- *Continuous abstinence rate from Week 9 through Week 24;*
- *Continuous abstinence rate from Week 9 through Week 52.*

6.2. Safety Endpoints

- *Adverse events spontaneously volunteered or elicited by the Neuropsychiatric Adverse Event Inventory (NAEI), Columbia Suicide Severity Rating Scale (C-SSRS), Hospital Anxiety and Depression Scale (HADS), safety laboratory tests, and vital signs.*

6.3. Windowing and Time Point Assignments

No windows will be used to determine planned weeks and days for this study. All analyses will be based on nominal day and week as recorded on the CRF. The exception will be the early termination visit. This visit will be assigned a nominal week according to the following windowing algorithm. (Note: The count of days starts from the first day of dosing and all intervals below are inclusive of the end days):

Week 1: day 2 through 10
Week 2: day 11 through 17
Week 3: day 18 through 24
Week 4: day 25 through 31
Week 5: day 32 through 38
Week 6: day 39 through 45
Week 7: day 46 through 52
Week 8: day 53 through 59
Week 9: day 60 through 66
Week 10: day 67 through 73
Week 11: day 74 through 80
Week 12: day 81 through 87
Week 13: day 88 through 94
Week 14: day 95 through 101
Week 15: day 102 through 108
Week 16: day 109 through 126
Week 20: day 127 through 147
Week 22: day 148 through 161
Week 24: day 162 through 182
Week 28: day 190 through 210
Week 32: day 218 through 238
Week 36: day 246 through 266
Week 40: day 274 through 294
Week 44: day 302 through 322
Week 48: day 330 through 350
Week 52: day 358 on

In the event of ties, the non “early termination” visit (i.e. the earlier visit) will be selected as the representative visit.

Day will be computed by subtracting the date of the first dose of study medication from the date of the evaluation. In order that the first day of dosing be defined as Day 1, one day will be added to this difference.

Baseline will be defined as the latest evaluation performed prior to the first dose of study medication.

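### The early-termination windows in SAP 6.3 leave 49 follow-up days without a nominal week and send days 148-161 to a Week 22 visit that neither document schedules

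*SAP*

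**What the plan says.** SAP 6.3 uses the CRF week as the general rule: "All analyses will be based on nominal day and week as recorded on the CRF". It then carves out one case: "The exception will be the early termination visit". That visit gets its week from a list of day windows counted from first dose as Day 1, and "all intervals below are inclusive of the end days". Four consecutive entries show the difficulty:

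- "Week 20: day 127 through 147"
- "Week 22: day 148 through 161"
- "Week 24: day 162 through 182"
- "Week 28: day 190 through 210"

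The follow-up schedule in SAP 2.1 reads: "Clinic visits will occur at Weeks 13-16 (inclusive), 20, 28, 36, 44, and 52". Telephone visits are at Weeks 24, 32, 40 and 48. Protocol Section 6.3 and the protocol's follow-up schedule agree, and none of them has a Week 22.

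Two analyses use the nominal week of an ET record in follow-up. SAP 8.2.4.2 calculates cigarette reduction at each visit and models it with visit and treatment-by-visit terms. SAP 8.1.2.2 sets an unstructured covariance for that model, with compound symmetry if it does not converge. SAP 8.2.6.7 summarises HADS change from baseline at each visit.

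**The concern.** A windowing algorithm should give every eligible record exactly one valid visit. Here an ET visit on some days gets no week, and on others it gets a week that is not in the schedule. These are the last observations on subjects who are leaving, so their handling should not be left to programming.

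With no default rule, a programmer could drop a gap-day record, move it to the nearest week, or call it Week 52 because the protocol's follow-up schedule combines Week 52 and early termination in one column. The choice could be made after the data are seen. Cigarette reduction at Weeks 24 and 52 is a named secondary endpoint, and ET records on days 155-161 and 351-357 lie next to those two time points.

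A Week 22 level in the repeated-measures model would also be odd in itself, since only ET records could fill it.

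**Working it through.** **Inputs.** The 26 windows in SAP 6.3; the visit schedule in SAP 2.1 and protocol Section 6.3; the covariance structure in SAP 8.1.2.2; the planned 300 subjects in protocol Section 9.1. The documents state no total of unassigned days, so there is no figure of theirs to reproduce.

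**Gaps.** Gap = next lower bound − previous upper bound − 1.

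| Between weeks | Bounds | Unassigned days | Length |
|---|---|---|---|
| 24 and 28 | 182, 190 | 183-189 | 7 |
| 28 and 32 | 210, 218 | 211-217 | 7 |
| 32 and 36 | 238, 246 | 239-245 | 7 |
| 36 and 40 | 266, 274 | 267-273 | 7 |
| 40 and 44 | 294, 302 | 295-301 | 7 |
| 44 and 48 | 322, 330 | 323-329 | 7 |
| 48 and 52 | 350, 358 | 351-357 | 7 |

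Total: 7 × 7 = 49 days. From day 2 to day 182 the windows are contiguous, and none overlap.

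**Share of follow-up.** Days 88 to 364 number 277. 49/277 = 17.7%. Days 148-161 add 14 days: 14/277 = 5.1%. Together, 63/277 = 22.7%.

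**Labels against the schedule.** The schedule has 25 post-baseline visits (Weeks 1-16, 20, 24, 28, 32, 36, 40, 44, 48, 52). Every one has a window. Of the 26 windows, only Week 22 has no visit.

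**Covariance.** An unstructured matrix for v visits has v(v+1)/2 parameters: 25 × 26/2 = 325 for the scheduled visits, and 26 × 27/2 = 351 if Week 22 is added. A subject with an ET visit has no later visit, so the eight covariances of Week 22 with Weeks 24, 28, 32, 36, 40, 44, 48 and 52 have no paired data.

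**Records affected, by assumption.** The documents give no dropout rate. Suppose 5% to 40% of 300 subjects (15 to 120) have an ET visit spread evenly over days 88-364. Unassigned: 15 × 49/277 = 2.7 to 120 × 49/277 = 21.2. Sent to Week 22: 15 × 14/277 = 0.8 to 120 × 14/277 = 6.1.

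**Reach.** Subjects who discontinue count as smokers from then on (SAP 5 and 7), so the primary endpoint and abstinence rates do not depend on the ET week. C-SSRS periods are set by dose dates (SAP 8.2.6.8). The HADS maximum on-treatment increase and shift to worst score are not by visit (SAP 8.2.6.7). That leaves cigarette reduction and the HADS change by visit.

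**HADS and telephone weeks.** HADS is not collected by telephone. The present windows for Weeks 24, 32, 40 and 48 cover 4 × 21 = 84 days, on which an ET HADS value goes to a week with no scheduled HADS. If those windows were simply widened to 28 days, this would become 4 × 28 = 112 days.

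**The case against.** The strongest case on the other side accepts the gaps and the label but holds that little follows from them.

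- **Few days touch an endpoint week.** With contiguous midpoint windows, only 14 of the 63 days move to a week at which cigarette reduction is an endpoint: 155-161 to Week 24 and 351-357 to Week 52. The other 49 can affect those contrasts only through the model. This stands.
- **A share of days is not a share of records.** This stands. Percentages of 25% (49 of days 162-357) or 30% (63 of days 148-357) can be obtained by starting the count later; follow-up from day 88 is the fairer base.
- **The spacing may be deliberate.** From Week 24 to Week 48 every window runs from 6 days before to 14 days after 7 × week, perhaps to avoid pulling ET visits forward. The SAP does not say so, and such a choice would still need a rule for the days left out.
- **One contiguous table would worsen HADS**, from 84 to 112 days in telephone weeks. This stands and shapes the fix.

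Two stronger readings are tempting. A reader might infer that ET data on all 63 days are lost. That is not so: days 148-161 are assigned, to a mislabelled week. A reader might also infer that Week 22 will break the repeated-measures model. The SAP does not list which visits enter it. If all 25 do, 325 covariance parameters for about 300 subjects are already fragile without Week 22, and no fit shows that Week 22 would be decisive.

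**Conclusion.** The defect is exact: 49 of 277 follow-up days (18%) have no window, and a further 14 map to a visit that neither document schedules. On a literal reading, gap-day ET records drop out of by-visit analyses and days 148-161 are misplaced. The effect is confined to the cigarette-reduction model and summaries and the descriptive follow-up HADS change by visit.

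If Week 22 enters the model as a visit level, its covariances with later visits cannot be estimated. That may, but need not, contribute to the compound-symmetry fallback.

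Under the assumed 5% to 40% ET rate and even timing, about 3 to 21 records would be unassigned and about 1 to 6 would go to Week 22. The actual dropout pattern could give other numbers. Severity: minor.

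**What to change.** Delete Week 22 and replace the follow-up windows from Week 20 on with two contiguous sets, cut at the midpoints between adjacent visits on a 7 × week scale (for example, (140 + 168)/2 = 154 between Weeks 20 and 24).

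| Week | NUI-based outcomes | HADS and other clinic-only assessments |
|---|---|---|
| 20 | 127-154 | 127-168 |
| 24 | 155-182 | none |
| 28 | 183-210 | 169-224 |
| 32 | 211-238 | none |
| 36 | 239-266 | 225-280 |
| 40 | 267-294 | none |
| 44 | 295-322 | 281-336 |
| 48 | 323-350 | none |
| 52 | 351 on | 337 on |

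This leaves no unassigned follow-up day, no window without a visit, and no ET HADS value in a telephone week. State also which visits enter the cigarette-reduction model.

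Keep the existing tie rule, which prefers the scheduled visit. It has a cost: an ET record that falls after an attended visit in the same window will not be used by visit. For NUI outcomes this concerns days 148-154 among the 63. For HADS it concerns days 148-161, 211-217, 267-273 and 323-329, or 14 + 21 = 35 of the 63, whenever the preceding clinic visit was attended.

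The other costs are two short tables instead of one, and some ET values assigned up to about four weeks from the nominal clinic week (for example, day 168 to Week 20: 168 − 140 = 28 days). No data collection changes.
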